Study Protocol and Statistical Analysis Plan

Evaluation of Retinal Microvascular Change That May Develop in After Open Globe Injury

NCT05771467

November 27, 2023

Objective: To evaluate the effect of open globe injury on anterior chamber, intraocular pressure measurements, retina and choroidal microvascular circulation in the unaffected eye; and to compare results among healthy age-matched individuals.

Methods: This prospective case-control study was approved by the local ethics committee of the Akdeniz University Faculty of Medicine (Approval Number: 2021-162) and the study was conducted in compliance with the ethical standards set out in the Declaration of Helsinki. Informed consent was obtained from the participants who agreed to participate in the study. All subjects underwent a comprehensive ophthalmologic examination, which included refractive error (Nidek ARK-700A, Nidek Co., Ltd, Gamagori, Japan), best corrected visual acuity (BCVA), IOP/Fully Automatic Tonometer, NIDEK NT-2000, Nidek Co., Ltd., Aichi, Japan), biometry and axial length (AL) (IOLMASTER 500, Carl Zeiss Meditec AG, Jena, Germany), slit-lamp examination of the anterior and posterior segments, Scheimflug Topography (Pentacam Oculus Optikgeräte GmbH, Wetzlar, Germany), and retinal and choroidal thickness and microvascular circulation of the retina and choroid were measured and recorded with Swept-Source Optical Coherence Tomography AngioTM (Topcon Corp, Japan). The BCVA was converted into the logarithm of minimal angle resolution (logMAR). Of the individuals included in the study, anterior chamber depth (ACD), anterior chamber volume (ACV), central corneal thickness (CCT), thinnest corneal thickness (TCT), astigmatism value (AST), corneal volume (CV), axial length (AL), spherical equivalent (SFEQ), intraocular lens power (ILP), VA (visual acuity), central retinal thickness (CRT), central choroidal thickness (CCT), superficial retinal circulation (SRC), deep retinal circulation (DRC) and choriocapillaris circulation (CC) data were recorded. The patients were followed for approximately six months, examined at one week, one month and three months after the trauma, and a total of three measurements were taken from the subjects. One measurement was taken from the control group.

Statistical Analysis Plan (SAP): Statistical analyzes were performed using the IBM SPSS package, version 23.0 (SPSS Inc., Chicago, IL, USA). The Shapiro-Wilk test was used to analyze the normality of sample distribution. To define the sample, normally distributed values are presented as means \pm standard deviation, and non-normally distributed values are presented as median (minimum–maximum). The two-way repeated measures ANOVA test was used to examine the time-dependent change of the data. For the analysis of independent data, the independent-sample t-test and Mann-Whitney U test were used. For the analysis of

correlation, Spearman's correlation coefficient was used. The results were evaluated at a 95% CI. A level of $p < 0.05$ was accepted as statistically significant.

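### Sex is neither a stated matching factor nor an adjustment term, so any sex imbalance between patients and controls would confound the patient-control difference

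*Combined protocol and SAP*

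**What the plan says.** The Objective is worded causally: "To evaluate the effect of open globe injury on anterior chamber, intraocular pressure measurements, retina and choroidal microvascular circulation in the unaffected eye". It adds a comparison group: "to compare results among healthy age-matched individuals". Age is the only matching factor mentioned, and the document does not describe how controls were recruited or matched.

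The Methods call this a prospective case-control study, so allocation is not randomised. On timing, the patients were examined at one week, one month and three months after the trauma: "a total of three measurements were taken from the subjects". For controls: "One measurement was taken from the control group". No pre-injury measurement is described.

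The SAP gives two routes to a conclusion about the fellow eye. For independent data, "the independent-sample t-test and Mann-Whitney U test were used". For change over time, "The two-way repeated measures ANOVA test was used to examine the time-dependent change of the data"; the two factors are not named. No covariate, regression, stratified or matched-pair analysis is planned. The threshold is p < 0.05. Sex is not mentioned as a matching factor, recorded item, stratifier or covariate.

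**The concern.** Without randomisation, the sex mix of the patients depends on who is injured, and the text as written does not tie the sex mix of the controls to it. A t-test or Mann-Whitney U test attributes the whole difference between the groups to group membership. If the male shares differ, and an outcome has a different level in men and women, part of that difference is due to sex but would be read as an effect of injury. It could equally mask a real effect.

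The patient-control comparison carries weight that the rest of the plan cannot take over. The first patient measurement comes one week after trauma. An effect that is established by then and stays constant leaves no trace in the change from one week to three months. Only the comparison with controls could show it. Confounding of this kind does not shrink with enrolment: the bias stays the same while the standard error falls, so the false-positive rate rises.

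**Working it through.** **No figure to reproduce.** The documents state no sample size, power, standard deviation, effect size or sex distribution. What follows is an illustration.

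**Inputs from the documents**
- Matching: age is the only factor mentioned (Objective).
- Between-group tests: unadjusted (SAP).
- Significance level: 0.05 (SAP). The number of sides is not stated; two-sided is assumed.

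**Inputs assumed**
- Gap in male share between patients and controls: 10 to 40 percentage points.
- Sex difference in an outcome: 0.2 to 0.5 SD.
- Equal groups of 30 or 60.
- No true effect of injury.

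**Step 1: bias.** In SD units, bias = (male share in patients − male share in controls) × sex difference.
- Low end: 0.10 × 0.2 = 0.02 SD.
- Middle: 0.20 × 0.5 = 0.10 SD.
- High end: 0.40 × 0.5 = 0.20 SD.
- Balanced sex mix: 0 × any sex difference = 0.

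**Step 2: false-positive rate.** With n per group, the noncentrality is bias / √(2/n). The rate is the probability that a noncentral t variable with 2n − 2 degrees of freedom falls outside the two-sided 5% limits.

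| Bias (SD) | Noncentrality, n = 30 | Type I error, n = 30 | Noncentrality, n = 60 | Type I error, n = 60 |
|---|---|---|---|---|
| 0 | 0 | 5.0% | 0 | 5.0% |
| 0.02 | 0.077 | 5.1% | 0.110 | 5.1% |
| 0.10 | 0.387 | 6.7% | 0.548 | 8.4% |
| 0.20 | 0.775 | 11.9% | 1.095 | 19.2% |

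Example: 0.20 / √(2/30) = 0.20 / 0.258 = 0.775. A normal approximation for the same case gives 12.1%, so the result does not depend on the choice of method.

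**Step 3: which analyses are exposed.** Suppose a patient's reading is the sum of a fixed level for that patient's sex, a time effect and noise. Subtracting the one-week reading from a later one removes the sex level, so within-patient change is not biased by it. In patient minus control, the sex level does not cancel unless the male shares agree. The repeated-measures ANOVA does not repair this comparison: it is assigned to change over time, and controls have one reading each, so they supply no change.

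**The case against.** The strongest reply is that matching on age alone is read from silence. The phrase is half a sentence in the Objective, not a selection rule, and sex may have been matched without being mentioned. That stands: a reader might infer that controls were deliberately left unmatched on sex, and the document does not say so. It does not remove the point, because a plan that mentions only age commits to nothing on sex, and the analysis offers no second line of defence.

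A reader might also infer from the list of recorded variables that sex was not collected. The list does not support this. It holds only ocular measurements and omits age as well, although age had to be known for matching.

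Next, neither an imbalance nor a sex effect can be shown. That also stands. The documents contain neither quantity for any outcome, including the retinal and choriocapillaris circulation measures. The upper figures of 11.9% and 19.2% need both assumptions at their extreme together, and at the low end the inflation is negligible.

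Finally, the plan includes an analysis that is free of this problem. Any effect that evolves between one week and three months is studied within patients, where a fixed sex difference in level cancels. It would therefore be wrong to say that the whole study is confounded by sex. What remains exposed is the comparison with controls.

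**Conclusion.** The point holds as a conditional weakness of the patient-control comparison. As written, neither the stated matching nor the planned tests protect that comparison from a difference in sex mix. Under the assumed ranges the bias is 0.02-0.20 SD, with type I error of about 5.1-11.9% at 30 per group and 5.1-19.2% at 60. The sex gap, the sex effect and the group sizes are all assumptions. If the sex mix is balanced, or an outcome does not differ by sex, the bias for that outcome is zero.

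The documents do not support the stronger claim that a sex bias is present in this study, or that it reaches the time-course results. The point deserves action because the remedy is nearly free and removes an alternative explanation for the only comparison that can show an early, persistent effect.

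**What to change.** State whether controls were matched on sex as well as age, and show the sex split by group.

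Base the patient-control conclusion on a linear model with group, age and sex, using transformed or ranked outcomes where the distribution is not normal. The t-test and Mann-Whitney results can stay as unadjusted companions.

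The document is written in the past tense, so the adjusted analysis is probably the only route still open. If control enrolment has not closed, also frequency-match controls to patients on sex.

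The cost is a model term or two, that is, one or two degrees of freedom per outcome. Sex should be available from clinic records (an assumption, since the document does not say), so no extra visit or measurement should be needed. Frequency matching would somewhat narrow the pool of eligible controls.

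### Do the six-month follow-up wording, the missing IOP entry and the doubled CCT label leave the analysis mis-specified?

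*Combined protocol and SAP*

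**What the plan says.** Three places in the combined protocol and SAP are involved.

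- **Follow-up (Methods).** The text gives a length of follow-up together with the visits, "The patients were followed for approximately six months, examined at one week, one month and three months after the trauma", and continues in the same sentence with their number: "a total of three measurements were taken from the subjects". For controls it says: "One measurement was taken from the control group".
- **IOP (Objective and Methods).** The Objective covers the anterior chamber together with "intraocular pressure measurements, retina and choroidal microvascular circulation in the unaffected eye". The Methods include tonometry, with a named device, in the examination of all subjects. The list of recorded data that follows does not contain IOP.
- **CCT (Methods).** The list has "central corneal thickness (CCT), thinnest corneal thickness (TCT" near its start and "central retinal thickness (CRT), central choroidal thickness (CCT" further on, so one abbreviation stands for a corneal and a choroidal measure.

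The Statistical Analysis Plan section applies its tests to the data in general. It names no outcome variable and no visit.

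**The concern.** Because the SAP section names neither variables nor time points, the Methods paragraph is the only place that defines them. Errors there could carry straight into the analysis, in three ways.

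1. If follow-up is described as six months but measurement stops at three, a report might present a three-month dataset as six-month evidence. A statement that nothing changed late, or that a change had recovered, would then lack data for the second half of the period.
2. If the recorded-data list is taken as the list of outcomes, IOP is an objective with no outcome attached. The list does contain items that the Objective does not mention, such as lens power and astigmatism. Reporting or dropping IOP after seeing the results would then look equally compatible with the plan.
3. A dataset column or table row labelled CCT could be read as either tissue, and the choroidal entry is the only choroidal thickness variable in the list.

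**Working it through.** The documents give no sample size, power or effect size, so there is no planned figure to reproduce. The check is a comparison of the text, with simple counts.

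**Time axis**
- Inputs (Methods): visits at one week, one month and three months; three measurements in total; stated follow-up about six months.
- Visits listed = 3 and measurements stated = 3, so measurements left for any later date = 3 − 3 = 0.
- Share of stated follow-up covered by measurement = 3 / 6 = 50%, taking the approximate six months at face value.
- The time factor for patients therefore has three levels, the last at three months. Neither the Objective nor the SAP section sets a six-month endpoint, contrast or claim. Controls are measured once, so nothing on their side depends on the length of follow-up.
- Reading the six months as clinical observation or as a slip gives the same dataset and the same three levels.

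**IOP**
- Entries in the recorded-data list, in order: ACD, ACV, CCT, TCT, AST, CV, AL, SFEQ, ILP, VA, CRT, CCT, SRC, DRC, CC. Total = 15; IOP entries = 0.
- Set against the Objective: the anterior chamber has ACD and ACV; retina and choroidal circulation have CRT, SRC, DRC and CC; IOP has none.
- The Methods introduce the list as what was recorded, not as what will be analysed. The SAP section does not refer to the list and names 0 variables, so the list does not act as a filter on analysis.
- IOP appears in two other places: as a named objective, and as a measurement made with a specified device in all subjects. An analyst working from the Objective would include it.

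**CCT label**
- CCT is the 3rd and the 12th of the 15 entries, so 2 of 15 items share a label and there are 14 distinct abbreviations.
- Each use is preceded by its full term. The first stands next to another corneal thickness and the second next to retinal thickness.
- The Methods attribute choroidal thickness to the swept-source OCT instrument, which further identifies the second variable.
- The abbreviation is not used after the list, so no statement in the document depends on guessing its meaning.

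**Effect on the analysis**
- Measurements lost or gained if the wording were corrected: 0.
- Tests changed: 0, since the repeated-measures ANOVA, the two-group tests and the correlation are stated without reference to any of these items.

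**The case for a change.** The strongest argument for acting is that this paragraph is the document's only specification. With no outcomes or visits named in the SAP section, an inconsistent sentence and an incomplete list have nothing to correct them. A named objective missing from the only list of variables gives some room for selective reporting, and the remedy would cost only a few words.

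Part of this stands. The wording is inconsistent, and the document never says what the six months refers to; that it means clinical observation after the last study measurement is only a possible reading. Outcome conclusions cannot reach beyond three months under any reading. It is also true that the list omits IOP and doubles a label.

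The consequences do not follow, however. The sentence that gives six months also gives every visit time and the measurement count, so a reader can see where the data end. Misreporting them would be a fault of the report, not an effect of following the plan. Dropping IOP would be visible against the Objective, which protects it better than a place in a list of recorded items would. Recording lens power and astigmatism from examinations already performed does no harm. The choroidal thickness entry cannot be called a main outcome, because the document ranks no outcomes and its Objective names choroidal circulation, not thickness.

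**Conclusion.** No change to the plan follows. The three observations are correct as readings of the text: about half of the stated follow-up has no measurement, 0 of 15 recorded items are IOP, and 2 of 15 share an abbreviation. They are clerical slips or missing detail, and the rest of the document settles each one well enough for analysis. Following the plan as written gives three patient time points ending at three months, an IOP measurement available for analysis, and two thickness variables identified by their full names. No estimate, test, error rate or conclusion would differ if the wording were tidied.

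This rests on three assumptions: that the stated total of three measurements is accurate, so no six-month data exist; that the IOP readings taken at examination were kept; and that the SAP section's reference to the data is not confined to the recorded-data list. Nothing in the document contradicts any of them. Describing outcomes as extending to three months, reporting IOP and giving choroidal thickness its own abbreviation are ordinary copy-editing when results are written up.

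### The patient-control comparison is planned without covariates, so any systematic axial-length difference between the groups would stay in the retinal and choroidal results

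*Combined protocol and SAP*

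**What the plan says.** The Methods describe "This prospective case-control study", and part of the Objective is "to compare results among healthy age-matched individuals". No other matching factor is given.

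The Methods also state that "All subjects underwent a comprehensive ophthalmologic examination", and axial length is one of its listed components. For the back of the eye, "central retinal thickness (CRT), central choroidal thickness (CCT), superficial retinal circulation (SRC), deep retinal circulation (DRC) and choriocapillaris circulation (CC) data were recorded". Patients were "examined at one week, one month and three months after the trauma, and a total of three measurements were taken from the subjects". For controls, "One measurement was taken from the control group".

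The SAP section names four inferential methods: two-way repeated measures ANOVA for change over time, the independent-sample t-test, the Mann-Whitney U test and Spearman correlation. For group comparisons it says "For the analysis of independent data, the independent-sample t-test and Mann-Whitney U test were used". It names no covariate, regression, analysis of covariance or stratification.

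**The concern.** Injury status forms the groups, so randomisation does not protect their comparability, and matching on age does not balance axial length. If axial length differs systematically between the groups and is related to a retinal or choroidal outcome, part of the observed difference reflects eye size and would be read as an effect of injury.

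No other planned method fills the gap. Controls have one measurement, so they have no time factor to contribute to the repeated measures ANOVA. Spearman correlation describes an association and does not adjust a group difference.

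The contrast carries weight because no measurement before injury is described. Patients are first seen at one week, so their own time course shows only what changes after that. A shift already present at one week can be seen only against controls.

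**Working it through.** **Inputs from the documents.** The tests, the single control measurement, the three patient visits and the 5% significance level. No sample size, effect size, SD or power is stated, so there is no figure to reproduce.

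**Assumed inputs.** Two-sided testing; n = 30 per group; true difference 0.6 SD where power is considered; systematic axial-length imbalance d of 0, 0.25 or 0.5 SD; within-group correlation r between outcome and axial length of 0, 0.3 or 0.6. The adjusted model contains group, age and axial length, with age unrelated to the outcome.

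**1. Bias of the unadjusted difference.** Bias = r × d, in outcome SDs. The standard error is √(2/30) = 0.258. False-positive rates come from the noncentral t distribution with 58 degrees of freedom.

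| d | r | Bias (SD) | Unadjusted false-positive rate |
|---|---|---|---|
| 0, or any | any, or 0 | 0 | 5.0% |
| 0.25 | 0.3 | 0.075 | 5.9% |
| 0.5 | 0.3 | 0.15 | 8.8% |
| 0.5 | 0.6 | 0.30 | 20.8% |

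For d = 0.5 and r = 0.6 the rate is 15.2% at 20 per group and 31.8% at 50. At a fixed imbalance, recruiting more subjects makes it worse. A simulation of 4,000 runs at n = 30, d = 0.5, r = 0.3 gave 8.9% for the t-test, 8.4% for Mann-Whitney U and 4.6% for the model adjusted for axial length.

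**2. Power of the unadjusted test for a true 0.6 SD difference.** Without bias: 63%.
- Bias against the effect: the apparent difference is 0.6 − 0.15 = 0.45 or 0.6 − 0.30 = 0.30 SD, and power falls to 40% or 21%.
- Bias with the effect: the apparent difference is 0.75 or 0.90 SD, and apparent power rises to about 81% or 93%. That gain is spurious, because the estimate is too large.

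**3. Cost of adjusting.** With two covariates, the expected variance inflation of the group difference is 1 + (2 + n·d²/2)/(2n − 5).
- Balanced: 1 + 2/55 = 1.036.
- d = 0.5: 1 + (2 + 3.75)/55 = 1.105 (1.104 to 1.105 by simulation).

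Adjustment gains precision only if (1 − r²) × inflation is below 1, that is, if r exceeds √(1 − 1/inflation). The break-even is 0.19 when balanced and 0.31 at d = 0.5.

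| | r = 0 | r = 0.3 | r = 0.6 |
|---|---|---|---|
| Adjusted power, balanced | 61% | 65% | 80% |
| Adjusted power, d = 0.5 | 58.5% | 62.6% | 77.6% |

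In simulation the adjusted test's false-positive rate was 5% at d = 0.5 for both r = 0.3 and r = 0.6.

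**The case against.** The t-test and Mann-Whitney U are valid for an unadjusted difference, and the plan neither contradicts itself nor states a figure that fails. Bias needs two links, an axial-length difference by injury status and a relation between axial length and the outcome, and the documents give neither. They offer no reason why the uninjured eyes of patients should be longer or shorter than those of controls. This stands. A reader might infer that the patient-control results are biased, but the documents do not support that.

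A reader might also infer that the plan could not reveal an imbalance. It could: axial length is among the recorded variables, and the planned two-group tests can be applied to it. Only the adjustment is missing.

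The larger false-positive rates depend on the less favourable inputs. At 0.25 SD and r = 0.3 the excess is under one percentage point. By chance alone, a gap of 0.5 SD would arise about 5% of the time at 30 per group. Adjustment can also lose power, as the r = 0 column shows.

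Finally, five outcomes at three visits make 15 further contrasts. Without a rule for which result governs, a second analysis adds freedom to choose. That is fair, and the fix has to supply the rule. What survives is that a non-randomised contrast is left open to an alternative explanation that data already collected could examine.

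**Conclusion.** The point holds as an inexpensive improvement. The SAP does not name the patient-control contrast in its sentence on independent data; that reading follows from the design and is the only one that fits. On it, the contrast has no covariate adjustment although axial length is available for everyone.

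The harm runs from none to the upper values tabulated, and where this study lies in that range cannot be known from the documents. It can run in either direction, hiding a true difference or exaggerating one. Only the between-group comparison is affected: change within patients is not, provided axial length in the uninjured eye is stable. Age is already handled by matching, so its inclusion mainly concerns precision.

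**What to change.** 1. Apply the planned two-group tests to axial length and report the group difference with its 95% CI.
2. Keep the planned tests. Beside them, for central retinal thickness, central choroidal thickness, and the superficial retinal, deep retinal and choriocapillaris circulation measures, report the patient-minus-control difference with 95% CI from a linear model with group, age and axial length. Use the one-week axial length for patients and the single value for controls. Check residuals, and use a transformation or a robust CI where they are clearly non-normal.
3. State in advance that the one-week contrast is the main one and later visits are supportive. Where the two analyses disagree, the conclusion follows the adjusted estimate and the disagreement is reported.
4. State the assumption that injury does not alter axial length in the uninjured eye. Do not adjust axial length, spherical equivalent or lens power for axial length.
5. State whether matching was one-to-one. If so, include the pair as a random effect.
6. The text is in the past tense. If the data are already analysed, label the model post hoc and present it as a sensitivity analysis.

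**Cost.** No new data. The price is the variance inflation and break-even correlations shown in the working, plus two assumptions: a linear axial-length relation with the same slope in both groups, and no injury effect on axial length. Without a value from before the injury, patients' data cannot test the second.

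### Does the SAP leave the choice between the t-test and Mann-Whitney U, and the handling of non-normal outcomes in the repeated measures ANOVA, so open that results could suffer?

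*Combined protocol and SAP*

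**What the plan says.** The section Statistical Analysis Plan (SAP) is one paragraph. On normality it says "The Shapiro-Wilk test was used to analyze the normality of sample distribution". The only consequence it spells out is descriptive: normal values are summarised by mean and standard deviation, while "non-normally distributed values are presented as median" with the range. Two sentences on inference follow. For change over time, "The two-way repeated measures ANOVA test was used to examine the time-dependent change of the data". For comparisons between groups, "For the analysis of independent data, the independent-sample t-test and Mann-Whitney U test were used". Neither sentence is made conditional on the normality result. Correlation has a single method, Spearman, so no choice arises there.

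The Methods paragraph lists 15 recorded variables and gives the visit structure: "a total of three measurements were taken from the subjects. One measurement was taken from the control group". It contains no analysis rule. Neither section gives a sample size, a standard deviation or an expected difference.

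**The concern.** Read literally, the SAP offers two between-group tests and no rule for choosing between them. The two can fall on opposite sides of 0.05 for the same data, so some significance statements might depend on a choice that nobody wrote down, and a reader could not tell whether it was made before or after the results were seen. With 15 variables and three patient visits, the choice could arise 15 × 3 = 45 times.

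Two further gaps add to this. The SAP speaks of the sample distribution without saying whether that means each group, each visit or the pooled data. If it is judged visit by visit, one outcome could be tested or summarised on different scales at different visits. The SAP also expects some values to be non-normal, since it reserves a summary for them, yet names only ANOVA for change over time. What would be at stake is reproducibility and, at worst, some inflation of false positives.

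**Working it through.** The SAP has no figure of its own to reproduce here. The question is how much the unwritten details could change.

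**Inputs from the documents:** 15 variables, three patient visits and one control measurement (Methods); significance at p < 0.05 (SAP).

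**Assumed inputs:** 30 per group unless stated (20 and 50 also tried); outcomes normal or lognormal with log-SD 0.2 to 0.5; shifts of 0 to 0.7 SD; correlation between visits 0.8 or 0.95.

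**1. If the choice of test were wholly free.** At 30 per group the t-test and Mann-Whitney U disagree on significance in 1.9–3.3% of comparisons with no true difference, and in 7.1–12.1% with a 0.6 SD shift. Over all 45 comparisons the mean number of disagreements is 0.9–1.1 with no difference and 3.1–3.9 if every variable is shifted by 0.6 SD. Reporting whichever test is significant gives a type I error of 5.5–6.8%. This is the worst case, and it requires the normality test to play no part in the choice.

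**2. What the text implies.** In order, the SAP gives a normality test, two classes of values, and a parametric and a rank test for the same kind of comparison. The natural reading is the t-test when Shapiro-Wilk does not reject and Mann-Whitney U when it does. Only the unit of the normality check is then open.

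**3. How often the unit changes the test.** Three readings were compared: each group separately, the pooled sample, and within-group residuals. Part of their difference is arithmetic. For a truly normal outcome, one test at 0.05 rejects in 5.0% of cases, while at least one of two groups rejects in 1 − 0.95² = 9.75%. Simulated at 30 per group:

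| Outcome | Shift | Readings not all in agreement | t-test and Mann-Whitney disagree |
|---|---|---|---|
| Normal | 0 | 10.1% | 2.2% |
| Normal | 0.7 SD | 12.3% | 5.4% |
| Lognormal, log-SD 0.4 | 0 | 12.3% | 2.7% |
| Lognormal, log-SD 0.4 | 0.7 SD | 23.7% | 11.4% |

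**4. How often the unit changes the verdict.** Both things must happen in the same comparison: the readings pick different tests, and those tests disagree. If the two events were independent, the rate would be the product of the last two columns:

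- 0.101 × 0.022 = 0.2%
- 0.123 × 0.054 = 0.7%
- 0.123 × 0.027 = 0.3%
- 0.237 × 0.114 = 2.7%

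Independence is only an approximation, so the rate was also simulated directly. One run at 30 per group gave 0.2–1.5% for group-wise against pooled checking, and a second gave 0.3–2.1%. On the wider of these two ranges, 45 comparisons yield 45 × 0.003 = 0.1 to 45 × 0.021 = 0.9 altered verdicts. If only one visit is compared with controls, 15 comparisons yield 15 × 0.003 = 0.05 to 15 × 0.021 = 0.3.

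**5. Error rate of the two-stage rule.** Type I error was 4.8–5.6% in one run and 4.6–5.2% in another, against a nominal 5%.

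**6. The ANOVA.** Its normality assumption concerns residuals, so a raw variable that fails Shapiro-Wilk does not by itself rule the method out. For change within patients over three visits (30 patients, correlation 0.8 and 0.95, 20,000 trials), type I error was 5.1–5.2% for normal data and 4.5–5.1% for lognormal data with log-SD 0.2 and 0.5. A separate run gave 4.8–5.1%.

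**The case for a change.** The strongest reply is that an inferred convention is not a written one, and that without a unit it cannot be carried out in only one way. Two careful analysts could follow the SAP and print different tests for the same outcome. If normality were judged visit by visit, the selected test would differ between visits in 12% of normal outcomes and in 12–32% of lognormal ones (no true difference, correlation 0.8). Clarifying would cost two or three sentences.

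The factual part of this stands: the rule, the unit and the ANOVA handling are not written. The consequence does not follow at the size feared. A different test is seldom a different verdict, as step 4 shows. Switching between mean and median across visits would be untidy presentation, but each comparison would still be valid. The count of 45 is also an upper bound, because the documents do not say that patients are compared with controls at every visit.

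Nor does an alternative show a gain. Using the t-test for every outcome, with Mann-Whitney U as a sensitivity analysis, is defensible, but so is the convention the SAP implies. Asking that the ANOVA be judged on its residuals does not say what to do if they fail, so it would leave that gap where it is. Finally, the SAP is written in the past tense, so fixing choices in advance may no longer be possible.

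**Conclusion.** The concern does not call for a change. The SAP omits details that are conventionally understood. Filled in the ordinary way, its between-group comparisons keep their 5% level, and the one remaining ambiguity changes a significance verdict in roughly 0.3–2% of comparisons, fewer than one in the largest set the design allows. The ANOVA also holds its level under the skewness considered.

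These sizes rest on an assumed 30 per group, normal or lognormal outcomes and the stated correlations; the documents supply none of these. Outcomes with many tied values, such as visual acuity, were not simulated. For outcomes very far from normal the ambiguity tends to shrink, because every reading then rejects: at 50 per group with log-SD 0.4 and no shift, the three readings failed to agree in only 3.1% of datasets. How a second ANOVA factor is formed when controls are measured once is a separate matter that this check does not address. A sentence naming the rule and the basis for judging normality would be a courtesy to readers, but the soundness of the results does not depend on it.
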